- g A nasal swab will be collected for validated SARS-CoV-2 rapid antigen testing at Screening to confirm eligibility of participants for recruitment. Prior to each study vaccination, rapid antigen test results must be available for the determination of eligibility. Additional SARS-CoV-2 RT-PCR testing may be performed at planned or unscheduled visits in any participant who is being evaluated for risk of possible COVID-19 infection.
- h For contraindications for the second vaccination and criteria for vaccination delay, refer to Section 5.3.
- i Blood samples will be taken for neutralizing antibody testing before vaccine administration on Days 1 and 29 and on Day 181 for testing of immune responses to SARS-CoV-2 and future exploratory testing, including new emerging SARS-CoV-2 variants. In addition, blood samples may be used for safety testing in case of suspected myocarditis or other potential safety concerns. Blood samples for cardiac enzymes will be collected on Day 1 prior to vaccination (baseline) for all participants. The testing of baseline and post-vaccination samples for cardiac enzymes might be performed based on the investigator's or Sponsor's discretion. In case of early termination from the study due to safety reasons, a blood sample should be collected at the early termination visit. Collection of blood samples at unscheduled visits is at the investigator's discretion for evaluation of safety.
- j A baseline 12-lead ECG at recruitment will be performed on all study participants to identify potential asymptomatic myocarditis and pericarditis cases. In case of suspected myocarditis or pericarditis cases during the study period, detailed evaluation, including ECG, cardiac enzyme testing, and other relevant data should be evaluated. Additional ECG evaluation at unscheduled visits is at the investigator's discretion. Baseline ECG might be performed within 7 days prior to subject recruitment in the study.

CONFIDENTIAL

May not be used, divulged, published or otherwise disclosed without written consent of Arcturus Therapeutics, Inc.

Table 1 Schedule of Assessments

- k Study vaccines will be administered by intramuscular injection into the lateral area of the deltoid muscle of the opposite arms on Day 1. On Day 29, the study vaccine will be administered into the lateral area of the deltoid muscle of a non-dominant arm. Study vaccine will be administered in an observer-blinded fashion.

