8.12.3 Vaccination and Post-vaccination Procedures (Day 1 and Day 29)

Perform randomization ([Section 8.8](#)) at Visit 1 (Day 1).

After confirming eligibility ([Section 8.7](#)) at Visit 1 (Day 1) and at subsequent vaccination visit (Day 29), ensure that the participant does not meet criteria for delay or discontinuation ([Section 5.3](#)).

Perform vaccination ([Section 8.9](#)).

CONFIDENTIAL

The following post-vaccination procedures will be performed at Visit 1 (Day 1) and Visit 2 (Day 29):

- Participants will be observed for 30 minutes after vaccination in case of any adverse reaction. Any AEs reported within 30 minutes after vaccination will be recorded in the eCRF.
- After study vaccine administration, vital signs will be measured (BP, RR, body temperature, and heart rate) and vital sign measurement should be repeated if clinically indicated.

Careful training of the participant (or the individual who will be performing the measurements) on how to measure local reactions and body temperature, how to complete and how often to complete the eDiary will occur at Visit 1.

At Day 1, when two study vaccines will be co-administered, participant will be instructed to record local reactogenicity for both arms separately.

Specifically, participants in:

Groups 1a and 1b will receive: ARCT-2303 on the left arm and influenza vaccine on the right arm,

Groups 2a and 2b will receive: ARCT-2303 on the left arm and placebo on the right arm,

Groups 3a and 3b will receive: placebo on the left arm and influenza vaccine on the right arm.

At Day 29, vaccine administration will be done in the non-dominant arm.

eDiary instructions must include the following:

- The participant must understand that timely completion of the eDiary on a daily basis is a critical component to study participation.
- The participant should be instructed on how to complete the eDiary and how to make corrections to erroneous entries.
- Starting on the day of vaccination, the participant will check approximately 6 hours post-vaccination (minimum of 4 hours post-vaccination) for specific types of reactions at the injection site (solicited local adverse reactions), any specific generalized symptoms (solicited systemic AEs), body temperature (preferably axillary), any other symptoms or change in the participant's health status, and any medications taken.

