#### **Cohort A (participants 18 to 64 years of age; N=1200)**

Individuals will be randomly assigned to one of the three study groups:

[figure not shown]
- Group 1a (ARCT-2303/ Flucelvax Quadrivalent, N=400): participants will receive one dose of ARCT-2303 and one dose of Flucelvax Quadrivalent (opposite arms) on Day 1, and one dose of placebo on Day 29.
- Group 2a (ARCT-2303, N=400): participants will receive one dose of ARCT-2303 and one dose of placebo (opposite arms) on Day 1, and one dose of Flucelvax Quadrivalent on Day 29.
- Group 3a (Flucelvax Quadrivalent, N=400): participants will receive one dose of Flucelvax Quadrivalent and one dose of placebo (opposite arms) on Day 1, and one dose of ARCT-2303 on Day 29.

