#### 3.1 General Considerations

Data collected on the electronic case report form (eCRF) will be presented in the data listings for the second analysis (study end) and will be listed and sorted by cohort, treatment group, participant number and visit, where applicable. No individual listings will be generated at the first analyses (Day 57).

All safety and descriptive summaries will be presented by the treatment group and nominal visit/time point (where applicable). All disposition and concomitant medication descriptive summaries will be presented by treatment group.

Unless otherwise stated, the following methods will be applied:

- **Continuous variables**: Descriptive statistics will include the number of non-missing values (n), arithmetic mean, standard deviation (SD), median, minimum, and maximum values. The minimum and maximum values will be displayed to the same decimal precision as the source data, the arithmetic mean, SD, and median values will be displayed to one more decimal than the source data for the specific variable. 95% Confidence Intervals (CIs), mean differences (among treatments and from baseline) and least-square (LS-Means) values will be displayed to one more decimal than the source data for a specific variable. The appropriate precision for derived variables will be determined based on the precision of the data on which the derivations are based, and statistics will be presented in accordance with the above-mentioned rules. For source data with > 5 decimals, rounding to a maximum of 3 decimals will be performed.
- **Categorical variables**: Descriptive statistics will include counts and percentages per category. The denominator in all percentage calculations will be the number of participants in the relevant analysis population with non-missing data, unless specifically stated otherwise. Percentages will be displayed to one decimal place. Proportions will be displayed to 3 decimal places. 95% Confidence Intervals (CIs), differences, and other categorical parameters will be displayed to one decimal place for percentages. 95% Confidence Intervals (CIs) and differences in proportions will be displayed to 3 decimal places.

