#### **5.6 Treatment Exposure**

All study vaccine administration information on Day 1 and Day 29, including study vaccine administered (Yes/No), date and time of administration, location (left arm/right arm) will be presented in the by-participant data listings. Information on diary dispensation, activation and training will also be included in the same listings.

Number and percentage of participants who received each vaccine will be summarized by study group for the Safety analysis set, as described in section 3.1. Contraindications for the Second Vaccination will be presented in the by-participant data listings. Vaccination errors (or mis-dose) will be listed.

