### 7.1 Solicited Adverse Events

Information on Solicited Adverse Events will be summarized descriptively by treatment group, as described in section 3.1.

- Solicited local reactions and systemic AEs will be recorded daily within 7 days after each study vaccination:
  - Local reactions: pain, erythema and swelling at the injection site.
  - Systemic AEs: fatigue, headache, myalgia, arthralgia, nausea, dizziness, chills, and fever.

Severity grading for these AEs is presented in Table 1. Severity will be categorized programmatically as Mild, Moderate and Severe based on data collected on the eDiary and applying the definition provided in Table 1.

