- Solicited AEs during 7 days post Day 1 vaccination by reaction and grade

Implausible data values reported by the study participants in the electronic diary will be excluded from analysis (rule established before any planned analysis).

Implausible values are defined as:

- A measurement >200 mm for any local injection site erythema and swelling.
- A body temperature of <33°C and >43°C.

For the reported solicited local AEs from both arms after Day 29 vaccination: If a subject reports symptoms from different arms on different days, the symptoms should be combined; If a subject reports symptoms from both arms on the same day, only the data from the left arm will be analyzed and reported in the summary tables, and all solicited local AEs (from both left and right arms) will be presented in the reactogenicity listings (rule established before any planned analysis).

The following will be summarized by treatment groups:

- Use of antipyretics and analgesics will be summarized by frequency and percentage of participants reporting use.
- Body temperature will be summarized by 0.5°C increments from 38.0°C up to  $\geq 40.0^{\circ}$  C.

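### After the Day 29 dose, same-day reports from both arms are tabulated from the left arm only, which is the uninjected arm for anyone injected on the right

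*SAP*

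**What the plan says.** SAP Section 7.1 (text after Table 1) sets two rules for participants who report local symptoms in both arms after the Day 29 vaccination. Reports from different arms on different days are combined. For reports on the same day: "If a subject reports symptoms from both arms on the same day, only the data from the left arm will be analyzed". The right-arm entries then appear only in the reactogenicity listings. The SAP adds that the rule was fixed before any planned analysis.

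Four other places bear on this:

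- **Side of injection.** Protocol Table 1, footnote k: "On Day 29, the study vaccine will be administered into the lateral area of the deltoid muscle of a non-dominant arm". Protocol Section 8.12.3 agrees: "At Day 29, vaccine administration will be done in the non-dominant arm". The fixed left/right allocation in the same section is for Day 1.
- **One injection.** Every group receives a single injection on Day 29. For Group 3a the SAP's study design gives the Day 1 pair "and one dose of ARCT-2303 on Day 29".
- **Endpoint.** SAP Section 7.1 defines the local events as: "Local reactions: pain, erythema and swelling at the injection site".
- **Injected side on file.** SAP Section 5.6 covers Day 1 and Day 29 administration and states: "location (left arm/right arm) will be presented in the by-participant data listings".

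**The concern.** Whether the left arm is the injection site on Day 29 depends on the participant's dominant hand. The rule ignores this and always keeps the left. For someone injected on the right, a same-day two-arm report leads to the uninjected arm being tabulated as if it were the injection site, and the actual injection-site entry leaves the summary tables. That is not the endpoint the SAP defines.

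Local reactions within 7 days of each vaccination are part of the secondary safety objective. Groups 3a and 3b receive ARCT-2303 only on Day 29, so their local tolerability data for that vaccine come entirely from these tables. Listings that would show both arms are not produced at the first final analysis (SAP Sections 3.1 and 10.1), so a reader of the initial study report could not see the substitution.

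**Working it through.** The documents give no figure on this point, so the check compares the rules and then sizes the problem under stated assumptions.

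**Step 1. What the rule does, by injected arm and reporting pattern after Day 29**

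| Injected arm | Arms reported | What is tabulated | Correct arm? |
|---|---|---|---|
| Left | both, same day | left | yes |
| Right | both, same day | left | no: the uninjected arm is shown and the injection site omitted |
| Either | one arm only | that arm | not affected by the rule |
| Either | different arms, different days | both, combined | injected arm kept; can only over-count |

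The fault is confined to the second row.

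**Step 2. Effect on each output**

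- *Severity.* SAP Table 1 grades swelling of 25–50 mm as mild and 51–100 mm as moderate. With 60 mm on the injected right arm and 25 mm on the left, the rule tabulates mild where the injection site was moderate.
- *Incidence.* If both arms have the same symptom, the participant still counts under any severity. If a symptom is only in the injected right arm while the left arm has a different one, the right-arm symptom is lost for that day.
- *Duration.* SAP Section 7.1 takes the longest uninterrupted run. Suppose the rule is applied day by day, right-arm pain runs from day 1 to day 5, and the left arm has a different symptom on day 2. Day 2 of the pain is then dropped, the longest run is days 3–5, and duration falls from 5 days to 3.

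**Step 3. Size**

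From the documents: 1680 planned participants. On Day 29, 400 + 160 = 560 receive ARCT-2303 (Groups 3a/3b), 560 receive influenza vaccine (2a/2b) and 560 receive placebo (1a/1b).

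Assumed, because the documents do not give them: 5–15% injected on the right, and 1–10% of those reporting both arms on the same day.

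Participants at risk = group size × share injected on the right:

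- All: 1680 × 0.05 = 84 to 1680 × 0.15 = 252
- ARCT-2303 on Day 29: 560 × 0.05 = 28 to 560 × 0.15 = 84

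Participants affected = at risk × share with same-day two-arm reports:

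- All: 84 × 0.01 = 0.84 to 252 × 0.10 = 25.2, about 1 to 25
- ARCT-2303 on Day 29: 28 × 0.01 = 0.28 to 84 × 0.10 = 8.4, about 0 to 8

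Share of any group: 0.05 × 0.01 = 0.05% to 0.15 × 0.10 = 1.5%.

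**The case against.** The strongest reply is about size:

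- The tables are descriptive, and safety carries no hypothesis test.
- The main ARCT-2303 reactogenicity data come from Day 1, where 1120 participants (Groups 1a, 1b, 2a and 2b) receive the vaccine in a fixed arm and each arm is recorded separately.
- The 1.5% figure multiplies two assumed upper ends, and not every affected participant would be misclassified. If the rule works day by day, right-arm entries on days without a left-arm report still reach the tables, so the peak may survive.
- Protocol Section 8.12.3 also requires a solicited reaction to be entered on the AE form if it leads to a healthcare visit or withdrawal, is serious, or lasts beyond 7 days. Both arms appear in the listings at the second analysis, so no data are lost.
- A two-arm report after one injection may be a diary error, which puts the left/right labels in doubt.
- The rule was documented in advance, and replacing it has a cost.

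All of this stands as argument that the effect is small, and the 1.5% should be read as a ceiling under the assumptions, not a bound from the documents. None of it makes the left arm the injection site for someone injected on the right. Prespecification guards against choosing a rule after seeing results, but it does not make the rule match the endpoint. The injected-arm rule has the same protection, because the side is recorded as part of vaccine administration. The present rule relies on the same diary labels, so doubt about them does not favour it.

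**Conclusion.** The concern holds. For same-day two-arm reports after Day 29, the SAP rule contradicts the protocol's injection site and the SAP's own definition of a local reaction whenever the injection was on the right. That conclusion rests on the text alone.

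The size is small and rests on assumption: roughly 1–25 participants overall and 0–8 of the 560 receiving ARCT-2303 that day. A tabulated percentage would shift by at most about 1.5 points within the assumed ranges. The coprimary and secondary hypothesis tests and the Day 1 reactogenicity tables are unaffected. It should be corrected because the error is systematic, it falls on the only ARCT-2303 dose in two groups, and the information needed to avoid it is already held.

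**What to change.** Amend the same-day sentence in SAP Section 7.1: where both arms are reported on the same day after the Day 29 vaccination, tabulate the arm recorded as injected on Day 29 (the exposure data in Section 5.6), and use the left arm only if the injected side is missing. Leave single-arm reports, different-day reports and the both-arm listings as planned. A sensitivity summary applying the injected-arm rule to different-day reports is optional and not needed to resolve this point.

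The cost is one SAP sentence, a merge with exposure data already collected, and reprogramming of the Day 29 local-reaction tables, or a rerun if they already exist, which the documents do not say. No new data are needed. There are two drawbacks: the change still depends on participants labelling left and right correctly in the diary, and it replaces a rule that was documented in advance, so the amendment should state the reason.

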## 7.2 Unsolicited Adverse Events

All unsolicited AEs including SAEs, MAAEs and AESIs will be coded using MedDRA. Medical occurrences that begin before the study vaccination but after obtaining informed consent will be recorded in the medical history/current medical conditions section of the eCRF, not the AE section, all unsolicited AEs collected on the AE CRF page following the first administration will be considered TEAEs and will be included in the summaries.

Summary tables will include the number of participants (%) experiencing an event along with the number of events. Participants will be counted only once for each SOC and PT level (categorical descriptive analysis). All TEAE summaries will be presented by study group, SOC and PT.

The TEAE summaries will include:

- Overview summary of unsolicited AEs (Day 1 – Day 57)
- Summary of unsolicited AEs reported within 30 minutes after each study vaccination (derived by onset date time if event after vaccination date time) by SOC and PT. Please note that for Day 1, when 2 vaccinations are given, the 30 minutes interval is from the second vaccination.
- Summary of unsolicited AE within 28 days after each study vaccination by SOC and PT.
- Summary of related unsolicited AEs within 28 days after each study vaccination by SOC and PT
- Summary of unsolicited AE within 28 days after each study vaccination by SOC, PT and severity.
- Summary of related unsolicited AEs within 28 days after each study vaccination by SOC, PT and severity
- Summary of SAEs by SOC and PT
- Summary of related SAEs by SOC and PT
- Summary of SAEs by SOC, PT and severity
- Summary of related SAEs by SOC, PT and severity
- Summary of MAAEs by SOC and PT
- Summary of related MAAEs by SOC and PT
- Summary of AESIs by SOC and PT
- Summary of related AESIs by SOC and PT
- Summary of AEs leading to discontinuation from study by SOC and PT
- Summary of related AEs leading to discontinuation from study by SOC and PT
- Summary of (S)AEs with fatal outcome by SOC and PT

Additionally, the following summaries up to 28 days post Day 1 vaccination will be provided for Groups 2a and 2b combined (ARCT-2303), Groups 3a and 3b combined (QIV/aQIV):

- Summary of unsolicited AEs by SOC and PT
- Summary of related unsolicited AEs by SOC and PT
- Summary of SAEs by SOC and PT

For final analysis, summary of SAEs, MAAEs, AESI, AE leading to discontinuation and death will be presented cumulatively (Day 1 to EOS).

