- Hemagglutination Inhibition (HI) assay against influenza vaccine strains. In case of lack of agglutination for a specific strain using HI assay, immunogenicity for that strain will be assessed as measured by microneutralization (MN) assay;
- MN titers against influenza vaccine strains.

The results of HI and MN will be analyzed as:

- Geometric mean titer (GMT) on Days 1 and 29;
- Geometric mean-fold ratio (GMFR) as increases of the post-vaccination titer over the pre-vaccination titer;
- SCR on Day 29 as the percentage of participants in a group with either:
 - A pre-vaccination titer below the LLOQ for the respective assay and a post-vaccination titer $\geq 4 \times \text{LLOQ}$; or
 - A pre-vaccination titer $\geq \text{LLOQ}$ and a ≥ 4 -fold increase in post-vaccination titer.
- Proportion of participants with HI titer $\geq 1:10, 1:20, 1:40, 1:80, 1:160$ and $1:320$ on Days 1 and 29;
- Proportion of participants with MN titer $\geq 1:10, 1:20, 1:40, 1:80, 1:160$ and $1:320$ on Days 1 and 29.

CONFIDENTIAL

May not be used, divulged, published or otherwise disclosed without written consent of Arcturus Therapeutics, Inc.

Safety assessments:

- All participants will be monitored for 30 minutes after each study injection for any immediate post-vaccination adverse events (AEs) with appropriate medical treatment readily available in case it is needed.
- Solicited local reactions and systemic AEs will be recorded daily within 7 days after each study vaccination:
 - Local reactions: pain, erythema and swelling at the injection site.
 - Systemic AEs: fatigue, headache, myalgia, arthralgia, nausea, dizziness, chills, and fever.

On Day 1, when ARCT-2303 will be co-administered with the influenza vaccine, participants will be instructed to record local reactogenicity for both arms separately.

Specifically, participants in:

Group 1a and 1b will receive: ARCT-2303 on the left arm and influenza vaccine on the right arm

Group 2a and 2b will receive: ARCT-2303 on the left arm and placebo on the right arm

Group 3a and 3b will receive: placebo on the left arm and influenza vaccine on the right arm

- Any unsolicited AEs will be collected within 28 days after each study vaccination (from Day 1 to Day 29 and from Day 29 to Day 57).

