As of April 2023, most of the population in developed and low-and middle-income countries received primary vaccination and one booster dose of authorized COVID-19 vaccines. Overall, more than 13.3 billion doses of COVID-19 vaccines were distributed globally, and more than 5.1 billion people are considered fully vaccinated, according to the WHO ([Our World in Data, 2023](#)). In EU/EEA countries, 73.1% of individuals received the primary vaccination series, and 71% received at least one booster dose of COVID-19 vaccines ([European Centre for Disease Prevention and Control, 2023](#)). In the US, 84.6% of individuals completed the primary vaccination series, and 33.1% received a bivalent booster dose of the COVID-19 vaccine ([US CDC, 2023](#)). It is anticipated that, at the time of this study initiation, a significant proportion of the population will receive at least three doses of COVID-19 vaccines. To assess the immunogenicity and safety of ARCT-2303 in a homogeneous population,

CONFIDENTIAL

individuals who received the primary vaccination series and at least one booster dose will be recruited.

The study is active-controlled. At Day 1, all participants will receive 2 vaccine doses in opposite arms (ARCT-2303 and influenza vaccine, ARCT-2303 and placebo, or influenza vaccine and placebo). The assessment of immunogenicity will be performed 28 days after vaccination. To provide equal benefit from the participation in the study and complete seasonal vaccination against COVID-19 and influenza, a switchover vaccine dose (influenza, COVID-19, or placebo) will be administered on Day 29. It allows to keep the blinded design during the entire study period.

Due to the visual differences between the study vaccines, the participants will be blinded before receiving the injection in order to maintain the blinded design of the study. Therefore, the study includes measures to ensure study personnel remains blinded by assigning specific trained and unblinded medical personnel to administer the vaccine. See [Section 6.4](#) for more details.

The duration of immune response after booster vaccination with ARCT-2303 is unknown at the time of study initiation. As such, the kinetics of the immune response after the booster dose and antibody persistence will be assessed at 6 months after vaccination.

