9.1.6 Assessment of Outcome of AE

The investigator will assess the outcome of all AEs recorded during the study as:

- Recovered/resolved.
- Recovering/resolving.
- Not yet recovered/not yet resolved.
- Recovered with sequelae/resolved with sequelae.
- Fatal (all fatal events are considered SAEs and should be reported accordingly).
- Unknown.

9.1.7 Time Period and Frequency for Collecting Adverse Event and Serious Adverse Event Information

Medical occurrences that begin before the study vaccination but after obtaining informed consent will be recorded in the medical history/current medical conditions section of the eCRF, not the AE section. Exacerbation of a chronic or intermittent pre-existing condition including either an increase in frequency and/or intensity of the condition after the first vaccination will be considered an AE.

For all participants:

- Any unsolicited AEs will be collected within 28 days after each vaccination.
- Any AEs that occur within 30 minutes after study vaccination are to be reported in the eCRF.
- Any AEs that are determined by the investigator (or designee) to be SAEs, AESIs (serious and nonserious), MAAEs, or AEs leading to early termination from the study or
CONFIDENTIAL

study vaccination (regardless of the causal relationship) are to be reported in the eCRF from the moment of first vaccination until completion of the participant's last study-related procedure, which may include contact for safety follow-up (until the end of the study).

All AESIs and SAEs will be recorded and reported to the Sponsor or the Sponsor's designee immediately and under no circumstance should this exceed 24 hours after the investigator becomes aware of it. The investigator will submit any updated data to the Sponsor within 24 hours of it being available.

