10.3.3 Safety Analyses

The methods for the safety statistical analyses are described in [Table 10](#).

Table 10 Safety Analyses

| Endpoint | Statistical Analysis Methods |
|-----------|---|
| Secondary | 
Reactogenicity (solicited local and systemic AEs):
 
Percentages of participants experiencing each solicited AE will be summarized for each symptom by any (severity), maximum severity (mild, moderate or severe, except fever) during 7 days after vaccination by study arm. For the definition of severity grades, refer to Table 7.Duration and time of onset of events will be summarized by study arm descriptively by mean, SD etc.Injection site erythema and swelling will be summarized according to categories based on linear measurements.Use of antipyretics and analgesics will be summarized by frequency and percentage of participants reporting use.Body temperature will be summarized by 0.5°C increments from 38.0°C up to ≥40°C. In addition, fever will be summarized according to “mild”, “moderate” or “severe” categorization. 
Unsolicited AEs, SAEs, MAAEs, and AESIs:
 
Percentages of participants reporting at least one AE, related AE, SAE, MAAE, AESI within 28 days after each study vaccination will be summarized by study arm.Percentages of participants reporting at least one SAE, MAAE, AESI.Percentages of participant withdrawal/early termination from the study will be summarized by study arm.Percentages of participants reporting any AEs within 30 minutes after each study vaccination will be summarized by study group. 
AEs will be coded using the most recent version of MedDRA. AEs will be presented by SOC and PT by study group.
 
Data listings of all AEs will be provided by participant at final analysis.
 
All safety analyses will be performed on the SAF. Missing data will not be imputed.
 |

Abbreviations: AE, adverse event; AESI, adverse event of special interest; MAAE, medically attended adverse event; MedDRA, Medical Dictionary for Regulatory Activities; PT, preferred term; SAE, serious adverse event; SAF, safety analysis set; SD, standard deviation; SOC, system organ class.

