### 3.8 Treatment Groups

Group 1a: ARCT-2303 + QIV  
Group 2a: ARCT-2303 + Placebo  
Group 3a: QIV + Placebo  
Group 1b: ARCT-2303 + aQIV  
Group 2b: ARCT-2303 + Placebo  
Group 3b: aQIV + Placebo  
ARCT-2303 (Gr 2a and 2b)  
QIV/aQIV (Gr 3a and 3b)  
ARCT-154

If any actual treatments received cannot belong to any one of the treatment groups above (e.g. subject receives only one injection), the participant will be summarized under the randomized treatment group.

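### The Day 1 immediate-AE window in SAP 7.2 starts at the second injection, so an unsolicited AE with onset between the two injections is left out of the 30-minute summary

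*SAP*

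**What the plan says.** **Protocol.** Section 2.2.1 describes the Day 1 procedure: "At Day 1, all participants will receive 2 vaccine doses in opposite arms". The synopsis, under safety assessments, sets the observation period per injection: "All participants will be monitored for 30 minutes after each study injection for any immediate post-vaccination adverse events (AEs". Section 9.1.7 covers data capture: "Any AEs that occur within 30 minutes after study vaccination are to be reported in the eCRF". Table 10 in Section 10.3.3 plans the output: "Percentages of participants reporting any AEs within 30 minutes after each study vaccination will be summarized by study group".

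**SAP.** Section 7.2 lists the corresponding table as "Summary of unsolicited AEs reported within 30 minutes after each study vaccination (derived by onset date time if event after vaccination date time", tabulated by system organ class and preferred term. It then adds the Day 1 note: "Please note that for Day 1, when 2 vaccinations are given, the 30 minutes interval is from the second vaccination". Section 5.6 shows that the times needed are collected for each administration: "date and time of administration, location (left arm/right arm) will be presented in the by-participant data listings". Section 3.8 foresees a participant whose actual treatment fits none of the defined groups ("e.g. subject receives only one injection") and places that participant in the randomized group. It says nothing about time windows. Section 9 declares no changes to the planned analysis.

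**The concern.** The general rule in SAP 7.2 and the Day 1 note do not give the same window. The general rule counts events after each vaccination; the note moves the start of the Day 1 interval to the second injection. Because the derivation requires onset after the vaccination time, the period between the injections falls outside the window.

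That period matters for what the table is meant to show. Protocol Table 2 lists hypersensitivity, including anaphylaxis, first among the potential risks, says that allergic symptoms typically begin within a few minutes of vaccination, and gives the 30-minute observation as the mitigation. The first minutes after the first injection belong in such a table. The error also has a fixed direction: the rule can lower the Day 1 immediate-AE count or leave it unchanged, but cannot raise it.

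**Working it through.** The plan gives no figure to reproduce, so the check is a timeline comparison of the two rules.

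**Notation.** Let the first Day 1 injection be at time 0, the second at time g (minutes), and the AE onset at time e.

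**Windows when both injections are given**

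- Protocol, 30 minutes after each injection, for g up to 30 minutes: 0 < e ≤ g + 30.
- SAP 7.2 Day 1 note: g < e ≤ g + 30.
- Difference: 0 < e ≤ g. An event here is inside the protocol's window and outside the SAP's.

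The protocol window is g + 30 minutes long and the SAP window is 30 minutes long, so the part lost is g minutes. If both injections carry the same recorded time, g = 0 and nothing is lost. The documents fix the arm for each product on Day 1 but state neither the gap g nor the order of injection.

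**Only one injection given.** Here g does not exist, and the note can be read in two ways.

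- If its clause about two vaccinations is a condition, the note does not apply. The general rule then counts the event from the only injection.
- If the clause merely describes Day 1, the interval has no start time.

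The SAP does not say which is meant. Such a participant has received at least one dose and so belongs to the Exposed Set, from which the Safety Set is drawn (SAP 4.1.2 and 4.1.5). The question is therefore not settled by exclusion from the analysis set.

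**Where an event in the gap still appears.** SAP 7.2 treats every unsolicited AE recorded after the first administration as treatment-emergent and includes it in the summaries. An event with 0 < e ≤ g therefore stays in the overview and 28-day tables and, where it qualifies, in the related, severity, SAE, MAAE and AESI tables.

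**Whether its timing can be recovered.** Those tables do not show time from injection. SAP 3.1 and 10.1 provide for no individual listings at the first final analysis, which covers Day 1 to Day 57 safety. Listings come with the second final analysis, and only then could a reader compare onset with administration time.

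**Whether the departure is declared.** No other SAP text returns the gap to the immediate-AE table, and Section 9 reports no change.

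**The case against.** **The protocol may mean the visit, not the injection.** The protocol often uses the term study vaccination for the vaccination visit: the synopsis ties the unsolicited-AE windows to Day 1 and Day 29, and Table 1 labels the visits as first and second vaccination. On that reading Table 10 asks for AEs within 30 minutes after each visit's vaccination, and the SAP note only picks an anchor time for a two-injection visit. The per-injection wording in the synopsis would then describe clinical monitoring and not the table. This reading is fair and softens the conflict, but it does not remove the problem. An anchor at the second injection still loses events that follow the first injection of the same visit.

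**The event is not lost to safety reporting.** This stands. Collection in the eCRF is unaffected, and anaphylaxis is a listed AESI (Protocol Table 13) with reporting to the sponsor within 24 hours (Protocol 9.1.7). A reader might infer that the most serious immediate reactions disappear from the report. They do not; at most they lose their place in one table, and with it their label as immediate.

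**A reaction that prevents the second injection.** A reader might infer that such an event certainly drops out. The documents do not support this. The note is worded for the case of two vaccinations, so the general rule may cover a participant with only one. SAP 3.8 concerns group assignment and does not settle the matter. The accurate statement is that the SAP is not clear here.

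**Conclusion.** The point holds, and it is minor. Under the literal rule in SAP 7.2, an unsolicited AE with onset between the two Day 1 injections is omitted from the immediate-AE summary, and the start time for a participant with a single Day 1 injection is not clearly defined. The safety analysis is descriptive (Protocol 10.1), so no hypothesis test and no immunogenicity conclusion depends on this table.

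The number of events affected cannot be computed. It depends on the gap between injections and on the rate of AEs in that gap, and the documents give neither. It is probably small, on the assumption that the two injections are given close together.

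Two stronger readings should be resisted.

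- **An expected count.** Protocol Table 2 reports twelve hypersensitivity cases in more than 17,000 participants. A reader might scale this to the trial: 12 / 17,000 × 1680 = 1.2. That is not an estimate of the loss. The twelve cases have no stated timing and come from an earlier phase 1/2/3 study, not from this trial. Also, only 1120 participants (400 + 400 + 160 + 160) are due ARCT-2303 on Day 1, which would give 12 / 17,000 × 1120 = 0.8. Even that would count all such cases, not those that begin between two injections.
- **A bias toward one product.** A reader might infer that the loss falls on whichever vaccine is given first. The order of injection is not stated in the documents, and administration instructions are referred to a Pharmacy Manual that is not among them. Nothing can be said about which product is affected.

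**What to change.** In SAP 7.2, replace the Day 1 note with a definition such as: the Day 1 immediate-AE window runs from the time of the first injection to 30 minutes after the last injection actually received. For a participant with one Day 1 injection, the first and last injection are the same, so the window is the 30 minutes after it and no separate rule is needed.

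The cost is one sentence and a small change to the derivation. The administration times are already collected (SAP 5.6). The new window contains everything that the present one counts, so no event now reported would be lost. If the intention of the note was only to extend the window past the second injection, this wording states that intention. If the sponsor prefers to keep the present rule, a footnote to the table should say that the time between the two injections is not covered, and SAP Section 9 should record the difference from the protocol.
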